## 1. BACKGROUND AND RATIONALE

### 1.1. Hyaluronidases and rHuPH20

Mammalian hyaluronidase preparations differing in source, species, and manufacturing process have been the subject of multiple investigations and regulatory approvals in Europe, the United States, and Asia. The extent of human administration of these products in the U.S. has been estimated to be in the tens of millions of patients. Additionally, patients have been treated with other regulatory-approved preparations of hyaluronidase in Europe and Asia. Collectively, this usage spans nearly 60 years of clinical history in humans.

The U.S. Food and Drug Administration (FDA) contracted a review of the efficacy and safety of several hyaluronidase drug products through a program known as the Drug Efficacy Study Implementation (DESI). The studies were conducted by the National Academy of Sciences and the National Research Council. The DESI review findings published in the (Federal Register Sept 1970) established that hyaluronidase injection was “effective” for the following indications: For use as an adjunct to increase the absorption and dispersion of other injected drugs; for hypodermoclysis [subcutaneous fluid administration]; as an adjunct in subcutaneous urography; for improving the resorption of radiopaque agents.

The hyaluronidase drugs included in the DESI reviews included injectable hyaluronidase preparation derived from bovine testes. Replacing animal-derived slaughterhouse products with recombinant human biotechnology-developed materials potentially alleviates risks associated with animal pathogens, transmissible spongiform encephalopathies, and allergy and immunogenicity to foreign proteins.

rHuPH20 is a 447-amino acid single chain polypeptide with N-linked and O-linked glycan structures. rHuPH20 is synthesized in Chinese hamster ovary (CHO) cells that have been transfected with a plasmid containing the DNA sequence encoding the GPI-anchor deleted human PH20 hyaluronidase. The protein is purified through a series of chromatographic steps that results in a purified protein with high specific activity. rHuPH20 is up to 100 times more pure than the reference standard, slaughterhouse-derived hyaluronidase product based on specific activity. rHuPH20 depolymerizes hyaluronan (HA) by hydrolysis of the  $\beta$ -1,4 linkage between the C1 position of N-acetyl glucosamine and the C4 position of glucuronic acid.

A drug product formulation of rHuPH20 (HYLENEX) obtained FDA approval on 2 December 2005. The approval indication is an adjuvant to increase absorption and dispersion of other injected drugs; for subcutaneous fluid administration; and as an adjunct in subcutaneous urography for improving resorption of radiopaque agents. HYLENEX was made available as saleable product beginning October 2006 and as of 31 December 2008 a total of 7,284 vials of HYLENEX had been sold. HYLENEX was made available through a product sampling program beginning June 2006, and as of 31 December 2008 a total of 4,384 vials had been received at physician offices. Thus, cumulative patient exposure from marketed HYLENEX product outside of clinical studies could be a high as 11,668 based on the total vials of saleable product and sample product distributed and the unit dose of 150 Units per treated patient.

Across 19 studies, a total of 525 study subjects had been enrolled as of December 31, 2008 among whom 510 subjects are known to have been exposed to at least one dose of HYLENEX/rHuPH20. Of the 510 subjects exposed to HYLENEX/rHuPH20 in clinical studies, 100 received an intradermal injection of a test dose of 15 Units of HYLENEX and 410 subjects received a subcutaneous (SC) injection of HYLENEX/rHuPH20 either immediately before or admixed with a co-injected drug or fluid administration. [Table 1](#) shows the cumulative number of subjects known to have been exposed according to the dose of HYLENEX/rHuPH20. There have been six studies to date in which at least some study subjects are known to have received more than a single exposure to HYLENEX: HZ2-07-03 (two doses per subject), 1838-003 (more than one dose permitted), HZ2-07-02 (a two-part study with some subjects participating in both parts), HZ2-07-04 (up to four doses per subject), HZ2-08-04 (up to six doses per subject) HZ2-08-05 (up to five doses). [Table 1](#) presents the completed HYLENEX/rHuPH20 clinical studies.

**Table 1: Cumulative Number of Subjects Exposed to rHuPH20 by Dose in Halozyme-Sponsored Clinical Studies**

Dose of rHuPH20 (Units)	Number of Subjects Exposed (N = 510 a )
15 b	100
150	236
240	13
288	4
300	12
750	16
1,152	4
1,500	15
1,600	3
3,000	4
3,200	3
6,000	6
6,400	3
12,000	17
12,800	6
24,000	30
36,000	4
48,000	6
96,000	6

a Note: Amongst the 38 subjects exposed to rHuPH20 in Study HZ2-07-02 and 8 subjects in HZ2-08-04, only the patient's highest dose from either study stage was included in this table. Eleven subjects exposed to HYLENEX in Study HZ2-08-05 were included among the total of 510 subjects. Their dose has not yet been verified and they are not listed in this table. Amongst the 38 subjects exposed to rHuPH20 in Study HZ2-07-02 and 8 subjects in HZ2-08-04, only the patient's highest dose from either study stage was included in this table. The 11 patients in Study 160602 were also included in the total of 510. However, their information was not included in the table since there was variability among each subject's dose between 1050-7800 U (based on U/g of IgG).

b The 15 Unit dose was an intradermal test dose; all other administration was subcutaneous.

The most commonly reported adverse events (AEs) have been self-limited, transient, localized injection/infusion site observations. Comparison of the nature and incidence of AEs for HYLENEX versus the saline placebo in the double-blinded, placebo-controlled study designs shows that, with few exceptions, there were no AEs clearly attributable to HYLENEX, and in general the AE profile for HYLENEX was similar to that for saline placebo. The clinical data have not prompted any consideration of changes to the HYLENEX product label. The Investigator is to refer to the rHuPH20 Investigator's Brochure (IB) Version 1.0 for all current safety information.

## 1.2. Eczema, Spongiosis, and the Role of Hyaluronan

Spongiosis is a characteristic histopathological feature in acute eczema. It is believed to be caused by the secondary loss of cohesion between epidermal cells due to the influx of tissue fluid into the epidermis. Serous exudate extends from the dermis; as it expands, epidermal cells remain in contact with each other only at the site of desmosomes, acquiring a stellate appearance and giving the epidermis a sponge-like morphology. Investigators have conducted research to better understand the pathogenesis of spongiosis, specifically to understand whether HA may have a functional role in its pathogenesis.

HA is a well-known component of the connective tissues, such as in the cartilage of joints and the dermis of the skin. In the human epidermis, Tammi and Wells have used hyaluronic-acid-binding protein (HABP) to localize HA in the matrix between keratinocytes in the middle and upper parts of the spinous layer. In addition, Sakai reported that even the normal stratum corneum contains HA supplied by keratinocytes.

In the process of assessing whether HA participates in epidermal hyperplasia, Maytin and colleagues delivered *Streptomyces* hyaluronidase (Strep H) topically to degrade epidermal HA and blunt the accumulation of epidermal HA after acetone application. Strep H significantly reduced epidermal HA levels and also significantly inhibited the development of epidermal hyperplasia. This reduction in epidermal thickness was not attributable to any decrease in keratinocyte proliferation, but rather to an apparent acceleration in terminal differentiation. Overall, the data showed that HA is a significant participant in the epidermal response to barrier injury.

Ohtani and colleagues conducted a series of experiments to clarify the mechanisms for the influx of tissue fluid into the epidermis and the loss of cohesion between keratinocytes in acute eczema that results in spongiosis. First, they demonstrated increased intercellular accumulation of HA in the spongiotic epidermis by immunohistochemical staining using HABP and augmented hyaluronan synthase 3 (HAS3) mRNA expression by spongiotic keratinocytes. Secondly, they showed that the epidermis where the intercellular space was strongly stained with HABP showed weaker expression of membrane E-cadherin. Thirdly, IL-4, IL-13, and IFN- $\gamma$  increased HA production, enhanced HAS3 mRNA expression, and decreased membrane E-cadherin expression by normal human epidermal keratinocytes in both low- and high Ca+ media. Lastly, they demonstrated that IL-4, IL-13, their combination, and IFN- $\gamma$  could induce intercellular space widening in the epidermis with increased HA accumulation and decreased E-cadherin expression. These results suggest that the augmented production of HA and the decreased E-cadherin expression by keratinocytes stimulated with IL-4/IL-13 or IFN  $\gamma$  cause spongiosis in acute eczema.

Based on these recent preclinical studies, HA appears to be directly involved in the pathogenesis of spongiosis. Further investigation is merited to better understand the role of hyaluronidase, more specifically, rHuPH20 in the prevention and treatment of spongiosis.

### **1.3. Rationale for Intra-dermal Injection of rHuPH20 in Subjects with Nickel Allergic Contact Dermatitis**

As discussed in the previous section, HA plays an important role in the pathogenesis of spongiosis, the characteristic histopathological feature in acute eczema. However, there are no clinical data in the current medical literature that demonstrate the safety and efficacy of hyaluronidase for the treatment of eczema. Eczema is one of the most common skin diseases affecting up to 20% of children and up to 3 % of adults. While mild cases can be treated with emollients alone, most cases require the use of pharmacologic interventions. Topical corticosteroids have been the mainstay of pharmacologic treatment for eczema. However due to potential side effects including both local effects (skin atrophy and pigmentary changes) and systemic effects (adrenal suppression) new topical modalities have been developed. The most efficacious of these topical agents have been the topical calcineurin inhibitors (TCIs), tacrolimus ointment and pimecrolimus cream^10. These were widely used until 2006 when the FDA issued a boxed warning due to rare cases of cutaneous and systemic malignancy. Thus there is a significant need for novel safe and effective topical therapies.

The dose of rHuPH20 selected for this proof of concept study (3,000 U/dose) is intended to model a future topical formulation of rHuPH20 that will provide controlled release of rHuPH20 into the epidermis through the stratum corneum. The intradermal administration of rHuPH20 in this study will not require diffusion through the stratum corneum, and it is therefore considered a more direct route of administration for this proof of concept study. While daily intradermal injection of 3,000 U of rHuPH20 in 0.25mL is not likely to provide sustained release of enzyme at the injection site, it is anticipated that this dose will be sufficient to temporarily depolymerize the hyaluronan present in the dermis and epithelium.

Doses of rHuPH20 in non-human primates up to approximately 3.6 million U/kg were well tolerated, and daily repeat subcutaneous dosing of 600,000 U/kg showed no histologic findings at the injection site. Additionally, in a Halozyme sponsored clinical study, 6 subjects received a single dose of rHuPH20 at a dose of 96,000 U which is greater than the expected cumulative dose in this clinical study.

rHuPH20 may prevent and treat acute contact dermatitis/eczema. Therefore, we propose to conduct this Phase II pilot study in subjects who have a + or ++ reaction (see [Appendix B](#)) to nickel sulfate as a model of spongiosis.

## 2. STUDY OBJECTIVES

### 2.1. Primary Objective

- Determine the treatment effect of rHuPH20 or placebo control injection on the exposure to topical nickel allergen (Treatment Regimens 1 and 2)
- Determine the time to onset and severity of the cutaneous reaction to nickel allergen after pre-treatment with rHuPH20 or placebo control (Treatment Regimen 2)
- Assess the safety and tolerability of the rHuPH20 injection

### 2.2. Secondary Objectives

- Proportion (%) of subjects who, with pre-treatment, have a  $\geq 1$  grade reduction of the cutaneous reaction to nickel sulfate in at least one patch region at 48 hours
- Proportion (%) of subjects with a  $\geq 1$  grade reduction of the cutaneous reaction to nickel sulfate in at least one patch region after treatment
- Proportion (%) of subjects that have a  $\geq 1$  grade reduction of the cutaneous reaction to nickel sulfate in at least one patch region at Days 2, 3, 4, or 5
- Safety and tolerability of the injection based on AEs, physical examinations, and vital signs

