##### **Treatment Regimen 1:**

This regimen will assess the treatment of contact allergy to nickel: At baseline, a single row of four patches (1, 2.5, or 5% nickel sulfate patches; determined for each subject during the Screening period) will be placed on the upper space on the upper back. After 48 hours, the patches will be removed and an assessment will be made of the reaction site as per the ICDRG scoring system. Each subject will receive in the center of the cutaneous reaction an ID syringe push bolus injection of either rHuPH20 or placebo control. Each injection will be administered once daily for 5 days. Prior to each daily injection, subjects will be evaluated for efficacy, safety, and tolerability. A final evaluation will be conducted 7 days after the last dose of study treatment.

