### **3.2. Duration Of Time On Study**

Study subjects will be screened (Visit 1) for eligibility within 21 days prior to receiving study drug. The baseline nickel allergy patch test must be administered no less than 14 days after the screening nickel allergy test.

- Visit 2 (Day 1) will consist of the nickel patch test (Treatment regimen 1) and pre-treatment and then the nickel patch test (Treatment regimen 2)
- Visit 3 (Day 3) is the day of first treatment dose and conducted 2 days (no less than 48 hours) after V2
- Visits 4-7 (Days 4-7) are dose days
- Visit 8 will be conducted seven days after the last dose

Therefore, the anticipated duration of time on study for a given subject, from Screening to completion of the study is up to 35 days.

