## **11. APPENDICES**

## APPENDIX A. STUDY SCHEDULE OF EVENTS

Event	Screening	Baseline	Treatment					Follow-up
	Day -21 to Day -14	Day 1	Day 3	Day 4	Day 5	Day 6	Day 7	Day 14
	VISIT 1	VISIT 2	VISIT 3	VISIT 4	VISIT 5	VISIT 6	VISIT 7	VISIT 8
Signed and Dated Informed Consent	X							
Inclusion/Exclusion Criteria	X	X						
Medical History	X							
Concomitant Medications a	X	X	X	X	X	X	X	X
Complete Physical Exam	X							
Vital Signs (Body temperature, BP, HR, Resp. rate)	X b	X	X	X	X	X	X	X
CBC c	X							
Pregnancy Test, Serum or Urine	X	X						
Targeted Physical Exam d		X	X	X	X	X	X	X
Physical Examination of the Administration Site e		X	X	X	X	X	X	X
Nickel Sulfate and Vehicle Control Patch Placement and Interpretation	X	X						
Dose Administration		X	X	X	X	X	X	
Test Area Assessment			X	X	X	X	X	X
Trans-epidermal Water Loss Assessment f		X	X	X	X			

Event	Screening	Baseline	Treatment					Follow-up
	Day -21 to Day -14	Day 1	Day 3	Day 4	Day 5	Day 6	Day 7	Day 14
	VISIT 1	VISIT 2	VISIT 3	VISIT 4	VISIT 5	VISIT 6	VISIT 7	VISIT 8
Digital Photographs of the Allergen Test Sites f		X	X	X	X			
Chromometer Images of the Allergen Test Sites f		X	X	X	X			
AE/Toxicity Assessment		X	X	X	X	X	X	X

a Con meds within 21 days prior to dosing and through the follow-up assessment on Visit 8/Day 14 to be recorded.

b Include body temperature at screening visit.

c WBC (with differential), Hgb, Hct, and platelets.

d Includes positives on a review of systems and follow-up of findings from previous physical examinations.

e Conducted immediately before patch administration, after dose administration (Treatment Regimen 2), immediately after patch removal, and prior to and 10 minutes post-dose on Study Days 3-7, and Day 14.

f To be conducted at Baseline and on Days 3-5 and includes subject questionnaire (Days 3-5).

**APPENDIX B. INTERNATIONAL CONTACT DERMATITIS RESEARCH GROUP [ICDRG] SCORING SCALE****International Contact Dermatitis Research Group Scoring Scale**

Score	Interpretation
?	Doubtful reaction; faint macular erythema only
+	Weak (nonvesicular) positive reaction; erythema infiltration, possibly papules
++	Strong (vesicular) positive reaction; erythema, infiltration, papules, vesicles
+++	Extreme positive reaction; bullous reaction
-	Negative reaction
IR	Irritant reaction of different types

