2. OBJECTIVES

The primary objectives of the study are:

- Determine the treatment effect of rHuPH20 or placebo control injection on the exposure to topical nickel allergen (Treatment Regimens 1 and 2)
- Determine the time to onset and severity of cutaneous reaction to nickel allergen after pre-treatment with rHuPH20 or placebo control (Treatment Regimen 2)
- Assess the safety and tolerability of the rHuPH20 injection

Secondary objectives include:

- Proportion (%) of subjects who, with pre-treatment, have a ≥ 1 grade reduction of the cutaneous reaction to nickel sulfate in at least one patch region at 48 hours
- Proportion (%) of subjects with a ≥ 1 grade reduction of the cutaneous reaction to nickel sulfate in at least one patch region after treatment
- Proportion (%) of subjects that have a ≥ 1 grade reduction of the cutaneous reaction to nickel sulfate in at least one patch region at Days 4, 5, 6, 7 and 14.
- Safety and tolerability of the injection based on AEs, physical examinations, and vital signs

Descriptive-Only parameters include:

- Chromometer readings of the allergen test sites on Day 1, Day 3 (48 hrs), Day 4 (72 hrs) and Day 5 (96 hrs) after the placement of the patches
- TEWL (Trans-epidermal water loss) assessment on Day 1, Day 3 (48 hrs), Day 4 (72 hrs) and Day 5 (96 hrs) after the placement of the patches

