8.2 Secondary Variables

Analyses of the secondary endpoints will be based on the grades shown in ICDRG table in Section 8.1.

For Treatment Regimen 1 and 2, proportion of subjects that have a ≥ 1 grade reduction of the cutaneous reaction to nickel sulfate in at least one patch region after treatment.

For Treatment Regimen 2, proportion of subjects that have a ≥ 1 grade reduction of the cutaneous reaction to nickel sulfate in at least one patch region at 48 hours (Day 3) will be assessed.

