8.4 Baseline Values

For analyses based on grades, each treatment region will be assigned its own baseline value. The baseline values for regions under Treatment Regimen 1 and 2 will be the values collected at Day 3.

The baseline values for TEWL measurements and Chromometer readings will be the assessments collected on Day 1.

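### The by-day responder proportion is defined on different days in the protocol (Days 2, 3, 4 or 5) and the SAP (Days 4, 5, 6, 7 and 14), and the reference score for Day 3 is unresolved

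*Protocol*

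**What the plan says.** Protocol 2.2 has three responder items. The third counts subjects with a fall of at least one grade "in at least one patch region at Days 2, 3, 4, or 5". SAP section 2 gives the corresponding item, otherwise in nearly the same words, as "in at least one patch region at Days 4, 5, 6, 7 and 14".

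The timetable is in Protocol 3.2 and Appendix A. After Day 1 the next visit is Day 3: "Visit 3 (Day 3) is the day of first treatment dose and conducted 2 days (no less than 48 hours) after V2". Patches stay on until then: "After 48 hours, the patches will be removed and an assessment will be made of the reaction site as per the ICDRG scoring system". The "Test Area Assessment" row of Appendix A is marked on Days 3, 4, 5, 6, 7 and 14.

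The protocol defines no baseline for grades. SAP 8.4 does: "The baseline values for regions under Treatment Regimen 1 and 2 will be the values collected at Day 3".

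Both documents also keep a 48-hour item for pre-treated sites, which exist only in Regimen 2. Protocol 2.2 asks for a "reduction of the cutaneous reaction to nickel sulfate in at least one patch region at 48 hours", and SAP 8.2 says a fall "in at least one patch region at 48 hours (Day 3) will be assessed".

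SAP 8.2 lists the after-treatment item and the 48-hour item but not the by-day item. SAP 9.1 leaves the responder proportion to a qualitative medical review and attaches no days to it.

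**The concern.** A responder proportion is fixed by three things: the days counted, the score each day is compared with, and whether one qualifying day is enough or each day is reported. For this objective the two documents disagree on the first, leave the third open, and between them produce a contradiction on the second.

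Two analysts working from the same data, one with the protocol and one with the SAP, could report different proportions under the same objective. The part of the SAP that should put the endpoint into practice does not settle it. With no formal comparison planned, the descriptive proportions are the evidence on this objective, so their definition should be fixed before the blind is broken.

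**Working it through.** There is no planned figure to reproduce. The documents give no response rate, effect size or power behind the 20 evaluable subjects, and this point does not depend on that number. The check is a comparison of day sets.

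| Study day | Visit (Protocol 3.2, App. A) | Site scored (App. A) | In Protocol 2.2 | In SAP 2 |
|---|---|---|---|---|
| 2 | no | no | yes | no |
| 3 | yes | yes (SAP baseline) | yes | no |
| 4 | yes | yes | yes | yes |
| 5 | yes | yes | yes | yes |
| 6 | yes | yes | no | yes |
| 7 | yes | yes | no | yes |
| 14 | yes | yes | no | yes |

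**Overlap.** The shared days are {4, 5} and the union is {2, 3, 4, 5, 6, 7, 14}, so 2 of 7. Days 2 and 3 appear only in the protocol list; Days 6, 7 and 14 appear only in the SAP list.

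**Usable days.** Of the 4 protocol days, 3 have a scheduled score (3, 4, 5) and 2 have a score after the SAP baseline (4, 5). All 5 SAP days have a score after baseline.

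**Day 3.** Under SAP 8.4 the change at a site on Day 3 is its Day 3 grade minus its Day 3 grade, which is 0. That can never reach one grade, so the proportion is 0% for both injection types whatever the data. The same holds for the Regimen 2 48-hour item in SAP 8.2, because 48 hours is Day 3. Either that item needs another reference score or it carries no information.

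**Could the protocol mean treatment days?** Injections after patch removal run on Days 3 to 7, so treatment day k is study day k + 2. Treatment days 2, 3, 4 and 5 are then study Days 4, 5, 6 and 7, which is the SAP list without Day 14. This fits well but remains an inference. Protocol 5.1.3 calls study Day 3 Treatment Day 3, and Protocol 4.4 numbers the treatment days 3 to 7, so the protocol's own usage points the other way.

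**Day 14.** It falls 14 − 7 = 7 days after the last dose and 14 − 3 = 11 days after patch removal. Scoring on that day was already in Appendix A; its use in this objective is what the SAP adds.

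**Or against and.** The protocol's *or* can mean a fall on any listed day. The SAP's *and* can mean one proportion per day. Neither document says which is meant.

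**The case against.** The strongest reply is that little turns on this. Protocol section 8 and SAP sections 4 and 9 plan no formal comparison. The responder proportion goes to a medical review, and the SAP table list contains no responder table. Listing 8 and Figure 1 show every site's score by day, so any day set can be recovered. All of this stands, and it limits the consequence. It does not remove the contradiction.

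Two stronger readings are tempting, and the documents do not support them.

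*Half of the protocol's days can never give a value.* Only Day 2, 1 of 4, is unobservable without conditions. Day 3 is scored, and its change is zero only once the SAP baseline is applied to a protocol that states none.

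*Day 14 hides a drug effect because both arms will have healed by then.*
- There are no arms. The comparison is within subject, with two rHuPH20 sites and two placebo sites in each regimen.
- No healing rate is given. Suppose 80–95% of placebo sites fall by a grade by Day 14 (an assumption). One responding site of two is then found in 1 − (1 − 0.80)² = 96% to 1 − (1 − 0.95)² = 99.75% of subjects, but only if the two sites respond independently. If they always agree, the figure stays at 80–95%.
- On the SAP 8.1 scale a site graded 0 or 1/2 on Day 3 cannot fall by a full grade, and a site graded 1 must become fully negative, so healing and response are not the same thing.
- Day 14 can mask Days 4 to 7 only if days are pooled. The SAP does not say they are, and SAP 9.1 displays scores day by day.

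**Conclusion.** The inconsistency is real and can be checked in the text. The same secondary objective has two day lists sharing 2 of 7 days, and the protocol list cannot be carried out as written if its numbers are study days. The Day 3 baseline also forces the planned 48-hour reduction in Regimen 2 to zero, so the SAP conflicts with itself there as well as with the protocol. If the protocol meant treatment days, the by-day mismatch shrinks to Day 14 alone, but the 48-hour problem and the any-day or each-day question remain.

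These findings rest on the documents' schedule and definitions and need no assumed rates. The size of any shift in the reported proportion cannot be calculated, because no response rates by day are given. The practical impact is limited: the study is a descriptive pilot and the underlying scores are listed in full. It should still be corrected, because the reported value depends on which document is followed.

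**What to change.** Write one definition and use it in Protocol 2.2, SAP 2 and SAP 8.2:

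- **Days:** study Days 4, 5, 6 and 7, all already scheduled scoring days after the SAP baseline.
- **Reporting:** one proportion for each day, by regimen and injection type. This settles *or* against *and*.
- **Reference:** the site's own Day 3 grade.
- **Day 14:** a separate follow-up value, not pooled with the on-treatment days.
- **Regimen 2 48-hour item:** a reference other than the site's own Day 3 grade, for example the same subject's placebo sites on Day 3, with a stated rule for combining the two placebo grades.

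The sponsor should also confirm whether the protocol's Days 2, 3, 4 or 5 were meant as treatment days, and record the answer.

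The cost is wording in both documents. Every score needed is already scheduled, so no visit, assessment or subject is added.
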